**Table 4: Dose Modification Guidelines for Drug Immune-Related AEs associated with epacadostat and pembrolizumab**

**General instructions for AEs associated with Pembrolizumab:**

1. Corticosteroid taper should be initiated upon AE improving to Grade 1 or less and continue to taper over at least 4 weeks.
2. For situations where pembrolizumab has been withheld, pembrolizumab can be resumed after AE has been reduced to Grade 1 or 0 and corticosteroid has been tapered. Pembrolizumab should be permanently discontinued if AE does not resolve within 12 weeks of last dose or corticosteroids cannot be reduced to  $\leq 10$  mg prednisone or equivalent per day within 12 weeks.
3. For severe and life-threatening irAEs, IV corticosteroid should be initiated first followed by oral steroid. Other immunosuppressive treatment should be initiated if irAEs cannot be controlled by corticosteroids.

*The below table represents guidelines and are not required management for immune-related AEs and can be implemented at the discretion of the investigator. Specialist referral (Endocrinology, Pulmonary, GI, etc) is encouraged if questions arise about appropriate management.*

**Note:** Unless listed below, Grade 1 for all disease groups: continue therapy, treat symptoms, close monitoring for worsening symptoms, educate patient to report worsening immediately, if worsens: Treat as Grade (G) 2 or 3/4.

Toxicity	Hold Treatment For Grade	Management + Timing for Restarting Treatment	Follow-up	Treatment Discontinuation
Type 1 diabetes mellitus (if new onset) or Hyperglycemia	Type 1 diabetes mellitus (if new onset, including diabetic ketoacidosis [DKA]) or <math>\geq</math> Grade 3 Hyperglycemia, if associated with ketosis (ketonuria) or metabolic acidosis (DKA)	
 
- Delay therapy for new onset Type 1 diabetes mellitus or Grade 3-4 hyperglycemia associated with evidence of beta cell failure.
 
- Insulin replacement therapy is recommended for Type I diabetes mellitus and for Grade 3-4 hyperglycemia associated with metabolic acidosis or ketonuria.
 
- Evaluate patients with serum glucose and a metabolic panel, urine ketones, glycosylated hemoglobin, and C-peptide.
 
- Resume therapy when patients are clinically and metabolically stable
 
	
_____
	
Discontinue Pembrolizumab and Epacadostat if not clinically and metabolically stable

Hyperthyroidism^1	Grade 2	
 
- Continue therapy.
 
- Non-selective beta blockers (e.g. propranolol) are suggested as initial therapy.
 
	
_____
	
_____

	Grade 3	
 
- Delay therapy
 
- Resume therapy with one dose reduction when toxicity resolves to Grade 0-1
 
-Treat with non-selective beta-blockers or thionamides as appropriate
 
- Treat with an initial dose of IV corticosteroid followed by oral corticosteroids. When symptoms improve to Grade 1 or less, steroid taper should be started and continued over no less than 4 weeks.
 
Replacement of appropriate hormones may be required as the steroid dose is tapered.
 
	
_____
	
Toxicity does not resolve within 12 weeks of last dose or inability to reduce corticosteroid to 10 mg or less of prednisone or equivalent per day within 12 weeks

		-Consider endocrine consult		
	Grade 4	
 
- Discontinue therapy permanently.
 
- Treat with an initial dose of IV corticosteroid followed by oral corticosteroids. When symptoms improve to Grade 1 or less, steroid taper should be started and continued over no less than 4 weeks.
 
- Consider endocrine consult
 
	_____	Permanently discontinue
Hypothyroidism^1	Grade 2-4	
 
- Continue therapy at same doses.
 
- Thyroid hormone replacement therapy, with levothyroxine or liothyronine, is indicated per standard of care.
 
-Consider endocrine consult for Grade 3-4
 
	_____	Discontinue Pembrolizumab and Epacadostat if not clinically and metabolically stable
Thyroid disorders can occur at any time during treatment. Monitor patients for changes in thyroid function (at the start of treatment, periodically during treatment, and as indicated based on clinical evaluation) and for clinical signs and symptoms of thyroid disorders				
Hypophysitis	Grade 2	
 
- Delay therapy
 
- 1.0 to 2.0 mg/kg/day methylprednisolone IV or IV equivalent and initiate hormonal replacement as clinically indicated
 
- Can resume once metabolically and clinically stable and on doses of steroids < 10mg/day prednisone equivalent.
 
- Consult endocrinology for all grades
 
	_____	Toxicity does not resolve within 12 weeks of last dose or inability to reduce corticosteroid to 10 mg or less of prednisone or equivalent per day within 12 weeks
	Grades 3-4	- Discontinue therapy permanently.	_____	Permanently discontinue

Suspicion of adrenal crisis (e.g. severe dehydration, hypotension, shock out of proportion to current illness)
		
 
- Delay therapy
 
- Rule out sepsis
 
- Stress dose of IV steroids with mineralocorticoid activity
 
- IV fluids
 
- Consult endocrinologist
 
- If adrenal crisis ruled out, then treat as above for symptomatic endocrinopathy.
 
- Can resume once metabolically and clinically stable and on doses of steroids < 10mg/day prednisone equivalent.
 
	
_____
	
_____

Diarrhea/Colitis
	
Grade 2  Diarrhea: 4-6 stools/day over baseline; IV fluids indicated < 24 hours (hrs); not interfering with ADL.  Colitis: abdominal pain; blood in stool
	
 
-Delay therapy for 5-7 days and reevaluate.
 
-Resume therapy with same dose when toxicity resolves to Grade 0-1
 
-Symptomatic treatment
 
-Drink liberal liquids if not feasible administer fluids via IV infusion
 
	
If improves for to grade 1:          - Resume therapy with same dose
 
If persists > 5-7 days or recur:          - 1.0-2.0 mg/kg/day methylprednisolone or oral equivalent          - When symptoms improve to grade 1, taper steroids over at least 4 weeks, consider prophylactic antibiotics for opportunistic infections, and resume therapy.
 
If worsens or persists >3-5 days with oral steroids:          - Treat as Grade 3/4
	
Toxicity does not resolve within 12 weeks of last dose or inability to reduce corticosteroid to 10 mg or less of prednisone or equivalent per day within 12 weeks

	
Grade 3  Diarrhea: >7 stools/day over baseline; IV fluids <math>\geq 24</math> hrs; interfering with ADL.  Colitis: severe abdominal pain, medical intervention indicated, peritoneal signs
	
 
- Delay therapy for 3-5 days and reevaluate.
 
-Resume therapy with one dose reduction when toxicity resolves to Grade 0-1.
 
- 1.0 to 2.0 mg/kg/day methylprednisolone IV or IV equivalent.
 
- Add prophylactic antibiotics for opportunistic infections
 
- Consider lower endoscopy
 
-Drink liberal liquids if not feasible administer fluids via IV infusion
 
	
If improves:                  - Continue steroids until grade 1, then taper over at least 4 weeks.
 
If persists > 3-5 days, or recurs after improvement:                  - GI referral, and consideration of Infliximab 5 mg/kg under supervision by gastroenterologist (if no contraindication)
 
Note: Infliximab should not be used in cases of perforation or sepsis
	
Toxicity does not resolve within 12 weeks of last dose or inability to reduce corticosteroid to 10 mg or less of prednisone or equivalent per day within 12 weeks

	
Grade 4                  life-threatening, perforation
	
 
- Discontinue therapy permanently.
 
- 1.0 to 2.0 mg/kg/day methylprednisolone IV or IV equivalent.
 
- Add prophylactic antibiotics for opportunistic infections
 
- Consider lower endoscopy
 
-Drink liberal liquids if not feasible administer fluids via IV infusion
 
	
If improves:                  - Continue steroids until grade 1, then taper over at least 4 Weeks.
 
If persists > 3-5 days, or recurs after improvement:                  - GI referral, and consideration of Infliximab 5 mg/kg under supervision by gastroenterologist (if no contraindication)
 
Note: Infliximab should not be used in cases of perforation or sepsis
	
Permanently discontinue

AST, ALT, or Increased Bilirubin
	
Grade 1                  AST or ALT > ULN TO 3.0 x ULN and/or T. bili > ULN - 1.5 x ULN
	
 
- Continue therapy
 
	
 
- Continue liver function tests (LFT) monitoring per protocol
 
	
	
Grade 2                  AST or ALT > 3.0 to <math>\leq 5</math> x ULN and/or T. bili > 1.5 to 3 x ULN
	
 
- Delay therapy for 5-7 days and reevaluate.
 
- Resume therapy with same dose when toxicity resolves to Grade 0-1
 
	
If returns to baseline:                  - Resume routine monitoring, resume therapy same dose.
 
If elevation persist > 5-7 days or worsen:
	
Toxicity does not resolve within 12 weeks of last dose

		
 
- Increase frequency of monitoring to every 3 days.
 
	
 
- 0.5-1.0 mg/kg/day methylprednisolone or oral equivalent and when LFT returns to grade 1 or baseline, a steroid taper should be started and continued over no less than 4 weeks, consider prophylactic antibiotics for opportunistic infections, and resume therapy with same dose.
 
	
	
Grade 3-4 AST or ALT > 5 x ULN and/or T. bili > 3 x ULN
	
 
- Discontinue therapy permanently (see exception below)a (Therapy may be delayed rather discontinued if AST/ALT ≤ 8 x ULN and T.bili ≤ 5 x ULN)
 
- Increase frequency of monitoring to every 1-2 days
 
- 1.0 to 2.0 mg/kg/day methylprednisolone IV or IV equivalent (The recommended starting dose for grade 4 hepatitis is 2 mg/kg/day methylprednisolone IV)
 
- Add prophylactic antibiotics for opportunistic infections
 
- Consult gastroenterologist
 
	
 
- 0.5-1.0 mg/kg/day methylprednisolone or oral equivalent and when LFT returns to grade 1 or baseline, a steroid taper should be started and continued over no less than 4 weeks, consider prophylactic antibiotics for opportunistic infections, and resume therapy with same dose.
 
 
If returns to grade 2:
 
 
- Taper steroids over at least 4 weeks
 
 
If does not improve in > 3-5 days, or worsens or rebounds:
 
 
- Add mycophenolate mofetil 1g twice daily (BID)
 
- If no response within an additional 3-5 days, consider other immunosuppressants per local guidelines.
 
	
Permanently discontinue


Neurological
	
Grade 2 Moderate symptoms; Limiting instrumental ADL
	
 
- Delay therapy.
 
- Resume therapy with same dose when toxicity resolves to Grade 0-1
 
- Treat symptoms per local guidelines
 
- Consider 0.5 to 1.0 mg/kg/day methylprednisolone IV or PO equivalent.
 
- If ≥ Grade 2 Neurologic AE consider Neurology consult and brain imaging
 
	
If improves to baseline:
 
 
- Resume therapy with same dose when toxicity resolves to Grade 0-1
 
 
If worsens:
 
 
- Treat as Grade 3-4
 
	
Toxicity does not resolve within 12 weeks of last dose or inability to reduce corticosteroid to 10 mg or less of prednisone or equivalent per day within 12 weeks

		
 
- Discontinue therapy
 
	
If improves to grade 2:
	
Permanently discontinue

	Grade 3-4 Severe symptoms; Limiting self-care ADL; Life- threatening	
 
- If <math>\geq</math> Grade 2 Neurologic AE consider Neurology consult and brain imaging
 
- Treat symptoms per local guidelines
 
- 1.0-2.0 mg/kg/day IV methylprednisolone or IV equivalent
 
- Add prophylactic antibiotics for opportunistic infections
 
	
 
- Taper steroids over at least 4 weeks
 
 
If worsens or atypical presentation:
 
 
- Consider IVIG or other immunosuppressive therapies per local guidelines.
 
	
Pneumonitis	Grade 1 Radiographic changes only	
 
- Consider delay of therapy
 
- Monitor for symptoms every 2-3 days
 
- Consider Pulmonary and Infectious Disease (ID) consults
 
	
 
- Re-image at least every 3 weeks
 
	_____
	Grade 2 Mild to moderate new symptoms	
 
- Delay therapy
 
-Resume therapy with same dose when toxicity resolves to Grade 0-1
 
- For recurrent Grade 2 Pneumonitis discontinue therapy
 
- Pulmonary and ID consults
 
- Monitor symptoms daily, consider hospitalization
 
- 1.0-2.0 mg/kg/day methylprednisolone IV or oral equivalent, followed by taper
 
- Add prophylactic antibiotics for opportunistic infections
 
- Consider bronchoscopy, lung biopsy
 
	
 
- Re-image every 1-3 days
 
 
If improves:
 
 
- When symptoms return to near baseline, taper steroids over at least 4 weeks and then resume therapy with same dose and consider prophylactic antibiotics
 
 
If not improving after 2 weeks or worsening:
 
 
- Treat as Grade 3-4
 
	
Toxicity does not resolve within 12 weeks of last dose or inability to reduce corticosteroid to 10 mg or less of prednisone or equivalent per day within 12 weeks

	Grade 3-4	
 
- Discontinue therapy
 
	
If improves to baseline:
 
 
- Taper steroids over at least 6 weeks
 
	
Permanently discontinue

	Severe new symptoms; New/worsening hypoxia; Life-threatening	
 
- Hospitalize
 
- Pulmonary and ID consults
 
- 2-4 mg/kg/day methylprednisolone IV or IV equivalent
 
- Add prophylactic antibiotics for opportunistic infections
 
- Consider bronchoscopy, lung biopsy
 
	If not improving after 48 hours or worsening: - Add additional immunosuppression (e.g. infliximab, cyclophosphamide, intravenous immunoglobulin (IVIG), or mycophenolate mofetil).	
Renal Failure or Nephritis	Grade 1 Creatinine > ULN and > than baseline but ≤ 1.5 x baseline	
 
- Continue therapy
 
- Monitor creatinine weekly
 
	If returns to baseline: - Resumes routine creatinine monitoring per protocol	_____
	Grade 2 Creatinine > 1.5 x baseline to 3.0 x ULN	
 
- Delay therapy
 
- Resume therapy with same dose when toxicity resolves to Grade 0-1
 
- Monitor Creatinine every 2-3 days
 
- 1.0 -2.0 mg/kg/day methylpredniolone IV or oral equivalent.
 
- Consider renal biopsy
 
	If returns to Grade 1: - Taper steroids over at least 4 weeks, consider prophylactic antibiotics for opportunistic infections, and resume therapy with same dose and routine creatinine monitoring.  If elevations persist > 7 days or worsen: - Treat as Grade 4	Toxicity does not resolve within 12 weeks of last dose or inability to reduce corticosteroid to 10 mg or less of prednisone or equivalent per day within 12 weeks
	Grade 3-4 Creatinine > 3 x baseline to > 6 x ULN	
 
- Discontinue therapy permanently
 
- Monitor Creatinine daily
 
- 1.0-2.0 mg/kg/day methylpredniolone IV or IV equivalent
 
- Consult nephrologist
 
- Consider renal biopsy
 
	If returns to grade 1: - Taper steroids over at least 4 weeks and add prophylactic antibiotics for opportunistic infections.	Permanently discontinue

Skin	Grade 1 Covering < 10% body surface area (BSA)*	
 
- Continue therapy
 
- Symptomatic therapy (e.g. antihistamines, topical steroids)
 
	
If persists > 1-2 weeks or recurs:
 
 
- Continue therapy
 
- Consider skin biopsy
 
- Consider 0.5-1.0 mg/kg/day methylprednisolone IV or oral equivalent. Once improving, taper steroids over at least 4 weeks, consider prophylactic antibiotics for opportunistic infections.
 
	_____
	Grade 2 Covering 10-30% BSA*	
 
- Symptomatic therapy (e.g. antihistamines, topical steroids)
 
- Delay therapy for 1-2 weeks and reevaluate.
 
- Resume therapy with same dose when toxicity resolves to Grade 0-1
 
	
If persists > 1-2 weeks or recurs:
 
 
- Consider skin biopsy
 
- Delay therapy
 
- Consider 0.5-1.0 mg/kg/day methylprednisolone IV or oral equivalent. Once improving, taper steroids over at least 4 weeks, consider prophylactic antibiotics for opportunistic infections, and resume therapy with same dose
 
 
If worsens:
 
 
- Treat as Grade 3-4
 
	Toxicity does not resolve within 12 weeks of last dose or inability to reduce corticosteroid to 10 mg or less of prednisone or equivalent per day within 12 weeks
	Grade 3 Covering > 30% BSA	
 
- Delay treatment and consider oral steroids if necessary.
 
- Resume therapy with one dose reduction when toxicity resolves to Grade 0-1
 
- If the rash is grade 3 only based on BSA, and is otherwise mild and responds to dose interruption and topical steroids, can consider resuming at the same dose.
 
- Consider skin biopsy
 
	
If improves to grade 1:
 
 
- Taper steroids over at least 4 weeks and add prophylactic antibiotics for opportunistic infections
 
- Resume therapy with one dose reduction when toxicity resolves to Grade 0-1
 
	Toxicity does not resolve within 12 weeks of last dose or inability to reduce corticosteroid to 10 mg or less of prednisone or equivalent per day within 12 weeks

		
 
- Dermatology consult
 
- 1.0-2.0 mg/kg/day IV methylprednisolone or IV equivalent
 
		
	
Grade 4 Any % BSA; Life-threatening consequences (Refer to NCI CTCAE v5 for term-specific grading criteria)
	
 
- Discontinue therapy permanently
 
- Consider skin biopsy
 
- Dermatology consult
 
- 1.0-2.0 mg/kg/day IV methylprednisolone or IV equivalent
 
	Permanently discontinue	Permanently discontinue
Myocarditis	
Grade 1 or 2
	
 
- Delay therapy
 
- Administer corticosteroids
 
	_____	Toxicity does not resolve within 12 weeks of last dose or inability to reduce corticosteroid to 10 mg or less of prednisone or equivalent per day within 12 weeks
	
Grade 3 or 4
	
 
- Discontinue therapy permanently
 
- Administer corticosteroids
 
	Permanently Discontinue	Permanently Discontinue
All Other Drug-Related Toxicity c	
Grade 3 or Severe (meeting SAE criteria) or intolerable/persistent Grade 2
	
 
- Delay therapy
 
-Resume therapy with same dose when toxicity resolves to Grade 0-1
 
- Based on severity of AE administer corticosteroids
 
- If an SAE, consider dose reduction.
 
- Ensure adequate evaluation to confirm etiology or exclude other causes
 
	_____	Toxicity does not resolve within 12 weeks of last dose or inability to reduce corticosteroid to 10 mg or less of prednisone or equivalent per day within 12 weeks
	
Grade 4 or recurrent Grade 3
	
 
- Permanently discontinue
 
- Based on severity of AE administer corticosteroids
 
	_____	Permanently discontinue

		- Ensure adequate evaluation to confirm etiology or exclude other causes		
--	--	--	--	--

**Note: Permanently discontinue for any severe (meeting SAE criteria) or Grade 3 drug-related AE that recurs or any life-threatening event.**

**1. In general, for disease group GI, Hepatic, Endocrinopathy, Pulmonary, Renal, Neurological and skin:**

- Rule out non-inflammatory causes. If non-inflammatory causes are identified, treat accordingly and continue I-O therapy.
- Patients on IV steroids may be switched to an equivalent dose of oral corticosteroids (e.g. prednisone) at start of tapering or earlier, once sustained clinical improvement is observed. Lower bioavailability of oral corticosteroids should be taken into account when switching to the equivalent dose of oral corticosteroids.

**For the below disease groups, also:**

- For Endocrinopathy AE management:  
Consider visual field testing, endocrinology consultation, and imaging.
- For GI AE management:  
Opiates/narcotics may mask symptoms of perforation. Infliximab should not be used in cases of perforation or sepsis.
- For Hepatic AE management:  
Consider imaging for obstruction.
- For Pulmonary AE management:  
Evaluate with imaging and pulmonary consultation.
- For Renal AE management:  
Patients on IV steroids may be switched to an equivalent dose of oral corticosteroids (e.g. prednisone) at start of tapering or earlier, once sustained clinical improvement is observed. Lower bioavailability of oral corticosteroids should be taken into account when switching to the equivalent dose of oral corticosteroids.

a For patients with liver metastasis who begin treatment with Grade 2 AST or ALT, if AST or ALT increases by greater than or equal to 50% relative to baseline and lasts for at least 1 week then patients should be discontinued.

b If symptoms resolve within one hour of stopping drug infusion, the infusion may be restarted at 50% of the original infusion rate (e.g., from 100 mL/hr to 50 mL/hr). Otherwise dosing will be held until symptoms resolve and the subject should be pre-medicated for the next scheduled dose.

c Patients with intolerable or persistent Grade 2 drug-related AE may delay study medication at physician discretion. Permanently discontinue study drug for persistent Grade 2 AEs for which treatment with study drug has been held, that do not recover to Grade 0-1 within 12 weeks of the last dose.

**Table 5: Dose Modification Guidelines for Non-immune Drug-Related Adverse Events**

Toxicity	Grade	Hold Treatment (Y/N)	Timing for Treatment Restart	Dose/Schedule for Treatment Restart		Discontinue Subject (After Consultation with Merck & Incyte)
				Epacadostat (INCB024360)	Pembrolizumab (MK-3475)	
Hematologic toxicity	1, 2	No	N/A	N/A	N/A	N/A
	3	Yes	Toxicity resolves to $\leq$ Grade 1 or baseline	First occurrence, restart at same dose. Second occurrence or more, reduce dose when resuming.	Restart at same dose and schedule. See Sections 4.10.4. and 6.3. for recommendations regarding immune-mediated AEs.	Toxicity does not resolve within 12 weeks of last infusion.
	4	Yes	N/A	N/A	N/A	Permanently discontinue
Non-hematologic toxicity, excluding immune related AEs in Table 4 Note: Exception to be treated to similar Grade 1 toxicity: 
 
Grade 2 alopecia
 
Grade 2 fatigue
 
Grade 3 rash in the absence of desquamation, no mucosal involvement, does not require
 
	1	No	N/A	N/A	N/A	N/A
	2	Consider holding for persistent symptoms	Toxicity resolves to $\leq$ Grade 1 or baseline	Reduce 1 dose level	Restart at same dose and schedule. See Sections 4.10.4. and 6.3. for recommendations regarding immune-mediated AEs.	Toxicity does not resolve within 12 weeks of last infusion
	3	Yes	Toxicity resolves to $\leq$ Grade 1 or baseline	Reduce 1 dose level	Restart at same dose and schedule. See Sections 4.10.4. and 6.3. for recommendations regarding immune-mediated AEs.	Toxicity does not resolve within 12 weeks of last dose or inability to reduce corticosteroid to 10 mg or less of prednisone or equivalent per day within 12 weeks

Toxicity	Grade	Hold Treatment (Y/N)	Timing for Treatment Restart	Dose/Schedule for Treatment Restart		Discontinue Subject (After Consultation with Merck & Incyte)
				Epacadostat (INCB024360)	Pembrolizumab (MK-3475)	
systemic steroids, and resolves to Grade 1 within 14 days  For additional information regarding AE with potential immune etiology, see Sections 4.10.4 and 6.3.	4	Yes	N/A	N/A	N/A	Permanently discontinue

*Note:* Subjects who experience a recurrence of the same severe or life-threatening AE at the same grade or greater with re-challenge of the combination should be discontinued from study treatment immediately and not re-challenged.

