## 6. DOSE MODIFICATIONS

### 6.1. Rationale for Dose Modification(s)

Subjects may require modification of epacadostat if necessitated by drug-related AEs, including irAEs; dose reductions of pembrolizumab are prohibited.

Epacadostat Dose Level Table	
Dose Level	Dose in mg
Starting Dose (0)	300mg BID
First Dose Reduction (-1)	200mg BID
Second Dose Reduction (-2)	100mg BID

Dosing interruptions are permitted in the case of medical / surgical events or logistical reasons not related to study therapy (e.g., elective surgery, unrelated medical events, patient vacation, and/or holidays). Subjects should be placed back on study therapy within 3 weeks (~ 21 days) of the scheduled interruption, unless otherwise discussed with Merck and Incyte. The reason for interruption should be documented in the patient's study record.

In some circumstances, it may be necessary to temporarily interrupt both study treatments as a result of AEs that may have an unclear relationship to study drug(s). Treatment with both study drugs should be withheld for drug-related Grade 4 hematologic toxicities, non-hematological toxicity  $\geq$  Grade 3 (including laboratory abnormalities), and severe or life-threatening AEs.

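### Section 6.1 and Tables 4 and 5 of Section 6.2 give incompatible instructions for three overlapping kinds of drug-related toxicity, so patients with similar events may be managed differently

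*Combined protocol and SAP*

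**What the plan says.** By heading, Table 4 in Section 6.2 covers immune-related events and Table 5 covers non-immune drug-related events. Table 4 describes itself as guidance to be applied at the investigator's discretion. Table 5's non-hematologic row leaves out the immune-related events of Table 4.

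- **Recurrent Grade 3 hematologic toxicity.** The Table 5 epacadostat cell reads "Second occurrence or more, reduce dose when resuming". The note closing the same table begins "Subjects who experience a recurrence of the same severe or life-threatening AE at the same grade or greater with re-challenge" and goes on to take those subjects off treatment at once and bar re-exposure. The note closing Table 4 reads "Permanently discontinue for any severe (meeting SAE criteria) or Grade 3 drug-related AE that recurs or any life-threatening event".
- **First Grade 3, or persistent Grade 2, non-hematologic toxicity.** Table 4's last row, All Other Drug-Related Toxicity, reads "Resume therapy with same dose when toxicity resolves to Grade 0-1" and adds that a reduction be considered if the event is an SAE. Table 5 reads "Reduce 1 dose level" at both Grade 2 and Grade 3.
- **Grade 3 rash.** Table 5 handles as Grade 1 a Grade 3 rash that has no desquamation or mucosal involvement and does not require "systemic steroids, and resolves to Grade 1 within 14 days". Grade 1 in that row means no hold. Section 6.1 withholds both drugs for non-hematologic toxicity at or above "Grade 3 (including laboratory abnormalities), and severe or life-threatening AEs". Table 4's Grade 3 skin row delays treatment and then says "Resume therapy with one dose reduction when toxicity resolves to Grade 0-1". It allows a same-dose restart, at discretion, for an otherwise mild rash that is Grade 3 on area alone.

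Section 12.3 summarises dose intensity by cycle and overall, and tabulates reductions and delays by reason.

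**The concern.** A toxicity table should lead two clinicians with the same patient to the same instruction. Here the instruction can depend on which line is read. In the hematologic case the choice is between continuing at a lower dose and stopping with re-challenge barred, which is a safety matter. In the other two cases the lines differ on the restart dose or on whether to hold at all.

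The same decisions supply the data for the safety and tolerability objective. If the rule behind a reduction, delay or stop is not fixed, the Section 12.3 summaries mix the tolerability of the doublet with the site's reading of the tables.

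**Working it through.** No figure in the plan is attached to this point, so the check is mainly a comparison of the passages.

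**(a) Recurrent Grade 3 hematologic event**

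1. After a first Grade 3 hematologic event, Table 5 restarts both drugs at the same dose. Table 4's catch-all row also restarts at the same dose. There is no conflict at this step, and the restart is a re-challenge with the combination.
2. Suppose the same Grade 3 event returns. Section 7.9 treats Grade 3 or 4 as severe, and Table 6 describes Grade 3 as severe or medically significant.
3. The Table 5 cell then reduces and resumes. The Table 5 note stops and bars re-challenge. Table 4's closing note, and the recurrent Grade 3 line of its catch-all row, stop permanently.
4. The cell and the first of these notes are in the same table, so the immune/non-immune split cannot separate them.

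**(b) First Grade 3 or persistent Grade 2 non-hematologic event**

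1. Table 5 excludes only the immune-related events of Table 4.
2. Table 4's catch-all row and closing note refer to drug-related events without an immune restriction.
3. An event not shown to be immune can therefore fall under both tables. Section 6.3 defines an immune-related event partly by unknown etiology, so attribution is a judgement.
4. One table restarts at the same dose, the other one level lower.

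**(c) Grade 3 rash**

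1. Against Section 6.1, the Table 5 exception conflicts whatever the attribution: no hold against withholding both drugs.
2. Against the Table 4 skin row, it conflicts only if the attribution is unclear, since an immune rash belongs to Table 4.
3. The exception requires resolution within 14 days, which is not known when the hold is decided.

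**Size of the difference for one patient**

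Section 6.1 gives dose levels of 300 and 200 mg BID, which are 600 and 400 mg/day. The ratio is 400/600 = 0.667, a 33% reduction. Over a 21-day cycle this is 12,600 against 8,400 mg.

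The following is an illustration only. Its assumptions are not in the documents: a 182-day window, one deciding event at day E = 42 or 84, a hold of H = 7 to 21 days, and full dosing before the event (in case (a), the hold for the first event is ignored).

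Relative dose intensity = [E × 300 + (182 − E − H) × restart dose] / (182 × 300)

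For E = 42 and H = 14:

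- same dose: (12,600 + 126 × 300)/54,600 = 0.923
- one level lower: (12,600 + 126 × 200)/54,600 = 0.692
- permanent stop: 12,600/54,600 = 0.231

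| Instruction followed | Range over E and H |
|---|---|
| No hold, same dose | 1.0 |
| Hold, same dose | 0.885 to 0.962 |
| Hold, one level lower | 0.667 to 0.795 |
| Permanent stop | 0.231 (day 42) or 0.462 (day 84) |

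Case (a) contrasts the last two rows and case (b) the second and third. Case (c) contrasts the first row with a hold; the Section 6.1 sentence sets no restart dose for it.

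**Design figures**

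Section 12.1 states 80% power for 30 patients, 20% against 39%, one-sided 10%. Rejecting at 10 or more patients progression-free at 6 months gives an exact alpha of 0.0611 and power of 0.7934, in line with the stated figure. None of these inputs involves the toxicity tables.

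**The case against.** **Scope.** The headings assign immune events to one table and the rest to the other. The catch-all row's instructions on corticosteroids and on confirming etiology make an immune-only reading plausible. That weakens (b) and the skin-row part of (c). It does not remove (b), because the row's wording is not so limited, and it does not touch (a) or the clash with Section 6.1.

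**Discretion.** Table 4 is not required management, so it is right to say only that patients may be managed differently. The disclaimer does not extend to Table 5 or Section 6.1.

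**The recurrence rules can partly coexist.** Table 5's cell counts occurrences, while its note concerns the same event. Two different hematologic events could follow the cell without meeting the note. Table 4 also glosses severe as meeting SAE criteria; if Table 5's note is read that way, the conflict inside Table 5 narrows to serious events. Table 4's note still names Grade 3 separately.

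**Specific over general.** The rash exception may be meant to override Section 6.1. Nothing says so.

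**Safeguards.** Table 6 requires advance approval from both suppliers for re-challenge after a serious, possibly drug-caused event, or where re-exposure poses significant added risk. Section 6.3 requires immediate discussion of Grade 2 or higher immune-related events. These reduce the hazard but do not say which instruction governs, and they need not cover a non-serious Grade 3 hematologic event.

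**Frequency.** A reader might take the 6 of 15 patients at 300 mg BID who interrupted epacadostat (Section 2.2.4) and project 12 of 30 affected here. That count covers interruptions for any AE, not Grade 3 decisions in the overlap. The Grade 3 or higher events listed there among 56 patients include none that is hematologic, and only two (mucosal inflammation and one neurologic event) outside the immune-related list. They are pooled over four epacadostat doses. Neither count gives a rate for the conflicted decisions.

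**Conclusion.** The contradictions are real and concern three separate event types, not one event handled in opposite ways throughout. The firmest is recurrent Grade 3 hematologic toxicity, where Table 5 disagrees with its own note as well as with Table 4. Next is the rash exception against Section 6.1. The catch-all row against Table 5's non-hematologic row depends on reading that row as worded, without an immune restriction.

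For an affected patient the difference is stop or resume in (a), 33% of the daily epacadostat dose after a first event at the starting dose in (b), and hold or no hold in (c). How many patients would be affected cannot be derived from the documents.

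A reader might infer that the primary analysis is compromised. The documents do not support that. The endpoint runs to progression or death, Section 4.6.2 continues imaging after discontinuation for other reasons, and sample size, alpha and power do not depend on these tables. The Section 12.3 summaries would still describe correctly what was given. What suffers is their interpretation as tolerability, and consistency in a safety decision. The latter is enough to require correction.

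**What to change.** Reconcile these passages so that each drug-related event falls under one consistent instruction:

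- Table 4: the catch-all row, the closing note and the Grade 3 skin row.
- Table 5: the hematologic Grade 3 cell, the non-hematologic Grade 2 and Grade 3 rows, the rash exception and the closing note.
- Section 6.1: the sentence on withholding both drugs.

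State whether Table 4's catch-all row and closing note cover all drug-related events or only immune-related ones. State how the 14-day resolution condition applies when the hold decision is made.

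Which rule applies in each case is for the sponsor and the drug suppliers to decide; this review takes no position. The cost is a wording amendment, agreement with both suppliers and site re-training. No extra visits, tests or patients are needed.
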